**5.4.4 End of Initial Trial Evaluation Visit**

The initial trial evaluation period will be a minimum of 3 days. At the end of the initial trial evaluation period, the subject will be evaluated for qualification for permanent implant. If the subject qualifies for permanent implant, the subject will exit the study and continue their treatment per the physician's standard of care.

If the subject does not qualify for permanent system implant after a minimum of 5 days, the subject may be re-programmed with tonic stimulation, per physician discretion, and may enter the extended trial evaluation period. The extended evaluation period must continue for an additional minimum of 3 days.

Subjects will be re-programmed by trained personnel and/or an Abbott representative using the Clinician Programmer. Subjects will be instructed how to use the Patient Controller to adjust stimulation as needed to produce the best results and to complete the Patient Trial Diary daily during the extended trial evaluation period

For subjects continuing with the extended trial evaluation period record the required information on the applicable CRF:

- NRS
- Patient satisfaction and PRP
- Stimulation assessment
- Subject's feedback
- Lead location
- Physician preference (if applicable- only after End of Initial Trial Period Visit for the last subject for a single site)
- Adverse events (if applicable)
- Deviations (if applicable)
- Withdrawal (if applicable)
- Death (if applicable)
- Qualify for permanent implant

Upload and attach the following documentation to the applicable CRF:

- Images

The subject will continue to complete the Patient Trial Diary daily during the extended trial evaluation period (if applicable). The subject will record areas of pain, stimulation therapy goals and percentage of pain relief. At the end of the extended trial evaluation period, the End of Trial Summary report will be submitted to the sponsor.

Subjects who do not continue with the extended trial evaluation will exit the study and continue their treatment per the physician's standard of care.

Record the required information on the applicable CRF:

- NRS
- Patient satisfaction and PRP
- Stimulation assessment
- Clinician assessment
- Lead location
- Adverse events (if applicable)
- Deviations (if applicable)
- Withdrawal (if applicable)
- Death (if applicable)
- Qualify for permanent implant

Upload and attach the following documentation to the applicable CRF:

- Images

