### 4.3.2 Secondary Endpoint

The secondary endpoint is the rate of physician preference for anatomic placement versus targeted placement at the end of the study.

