## 5.4 Scheduled Procedures

The Principal Investigator is responsible for ensuring all clinical investigation data are collected as required per CIP scheduled procedures.

The list of clinical investigation specific tests and procedures (Table 2) below summarize visit flow and requirements of this clinical investigation.

Table 2: List of all clinical investigation specific tests and procedures

Visit	Enrollment / Baseline	Trial System Implant (Initial Trial Evaluation Period Start)	End of Initial Trial Evaluation Period Begin Extended Trial Evaluation (if applicable)	End of Extended Trial Evaluation Period (if applicable)	Unscheduled Visit
Study Activity					
Informed Consent	X				
Subject Eligibility	X				
Demographics, Pain History & Diagnosis	X				
Numerical Rating Scale	X		X	(X)	

PROMIS-29	X				
Pain Catastrophizing Scale	X				
Patient satisfaction and PRP			X	(X)	
Randomization	X	(X)			
Implant procedure and system data		X			
Patient Trial Diary		X	X	(X)	
Email Programming Details		X	X	(X)	(X)
Stimulation Assessment		X	X	(X)	(X)
Qualify for permanent implant			X	(X)	
Reason for Visit					X
Procedure Time		X			
Programming Time		X			(X)
Subject's Feedback			X		
Clinician Assessment		X			
Physician's Preference			X*		
Imaging		X	X	(X)	(X)
Lead Location		X	X	(X)	(X)
SADEs, SAEs ADEs		(X)	(X)	(X)	(X)
Deviation(s)	(X)	(X)	(X)	(X)	(X)
Withdrawal	(X)	(X)	(X)	(X)	(X)
Death	(X)	(X)	(X)	(X)	(X)

(X) If applicable

\* only after last subject's last End of Initial Trial Period Visit- for a single site

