#### 5.4.2 Randomization and Blinding

Randomization may occur at the end of the baseline visit or just prior to surgery for trial system implant (Initial Trial Evaluation Period Start) Visit.

Subjects will be randomized (1:1) using random permuted blocks of varying length and stratified by site. Subjects will be blinded to treatment group and treated in two groups as follows:

1. Group 1 (AB): anatomic lead placement followed by BurstDR™ stimulation during initial trial evaluation period
2. Group 2 (TB): targeted lead placement followed by BurstDR™ stimulation during initial trial evaluation period

Randomization assignment will be communicated to the site via the Randomization Application available in the EDC Site Portal.

Regardless of sedation, subjects will not be able to distinguish what implant technique (anatomic or targeted) is utilized without intimate knowledge of SCS programming, and with standardizing subject

interactions, the subjects will remain blinded to the treatment group. Implanting physicians and surgical support staff must follow the specific guidelines for the lead placement techniques and therefore cannot be blinded, but will be provided with a standardized script to assist with subject interaction as a way to minimize the risk of disclosing randomization assignments. Additionally, sites will be instructed to schedule study visits to restrict study subjects from being in the clinic at the same time, which aims to minimize subject to subject communication. Prior to study exit and before being unblinded, subjects will be asked about their memory for intra-operative testing as an assessment of the blind. Intra-operative testing is the key distinguishing feature between the techniques, so assessment of memory for experience will help to establish the status of the blind for each subject.

A Blinding Plan will be maintained separately which will include a listing of all parties involved in the study to manage workflow and identification of blinded and unblinded information.

[figure not shown]

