## **5.7 Clinician Assessments**

The clinician assessment of the two lead implant techniques will be performed at the end of each trial implant procedure and again at the end of the study.

At the end of each trial implant procedure, clinicians will be asked to rate the magnitude of anesthesia-related difficulty experienced during the procedure, the magnitude of difficulty in placing the leads, and their affinity (liking) for the trial implant procedure performed compared to their usual practice.

Anesthesia-related difficulty and Lead Placement difficulty will be assessed with a 5-item Likert scales (No Difficulty, Little Difficulty, Moderate Difficulty, Severe Difficulty, Extreme Difficulty – could not place leads). To assess affinity (liking), clinicians will be asked: “On a scale from 0 to 4, with 0 being ‘not at all’ and 4 being ‘very much’, how much did you like this trial implant procedure compared to your usual clinical practice.” Scores will be treated as magnitude of “liking” for each procedure and will be tabulated as interval data.

At the end of the study, clinician’s comparative preference for one procedure over the other will be assessed; this will serve as the secondary endpoint. Clinicians will be asked to choose either “Anatomic Lead Placement” or “Targeted Lead Placement” in response to the following question: “Considering your subjects’ experiences and outcomes and your experiences with both lead placement techniques, which technique do you prefer?”

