#### Hypothesis:

[figure not shown]
The hypothesis is formally addressed as:

$H_0: P \leq 60\%$

$H_1: P > 60\%$

where P= percentage of physician prefer anatomic placement over targeted placement.

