### **6.3 Multiplicity**

There is one primary endpoint and one secondary endpoint of this clinical investigation. The secondary endpoint will be tested when the primary endpoint is met. Therefore, no multiplicity adjustment is needed.

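### Section 5.4.4 lists physician preference, the only tested secondary endpoint, solely for subjects entering the extended period, in conflict with Table 2, and the visible text does not say which physicians count

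*Combined protocol and SAP*

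**What the plan says.** **Role of the endpoint.** Section 4.3.2: "The secondary endpoint is the rate of physician preference for anatomic placement versus targeted placement at the end of the study". Section 6.1.2 tests H0: P ≤ 60% against H1: P > 60%, "where P= percentage of physician prefer anatomic placement over targeted placement". Section 6.3 makes the test conditional on the primary: "The secondary endpoint will be tested when the primary endpoint is met".

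**When it is recorded.** Table 2 in Section 5.4 marks the preference row at the end of the initial trial period, with the footnote "only after last subject's last End of Initial Trial Period Visit- for a single site". Section 5.7 has clinicians choose between the two techniques at the end of the study.

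**Where Section 5.4.4 puts it.** That section has two form lists. The first opens "For subjects continuing with the extended trial evaluation period record the required information on the applicable CRF" and includes "Physician preference (if applicable- only after End of Initial Trial Period Visit for the last subject for a single site". The second, for subjects who do not continue, has no preference item. It does include a clinician assessment.

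**Who answers.** The question in Section 5.7 appeals to "your experiences with both lead placement techniques". Section 5.4.2 randomizes with "random permuted blocks of varying length and stratified by site". Physician is not named as a stratum.

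**The concern.** The preference answer describes a physician, but the protocol collects it through the visit of one subject, the last at each site. In Section 5.4.4 the item appears only on the branch for subjects who did not qualify and were extended at the physician's discretion. Whether a physician's answer exists would then depend on one subject's outcome and on a later decision by the site.

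Two things are at stake. The only hypothesis test besides the primary could rest on a small subset of sites selected by outcome. In addition, without a stated set of respondents, the same answers can give different results depending on who is counted: one physician per site, every implanter, or only those who used both techniques.

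**Working it through.** The visible text gives no number of physicians, significance level or power for this endpoint, so there is no planned figure to reproduce. The check compares the texts and then illustrates the size under stated assumptions.

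**1. The texts side by side**

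| Place | When preference is recorded | Limited to extended-period subjects? |
|---|---|---|
| Section 4.3.2 | End of study | No |
| Section 5.7 | End of study | No |
| Table 2 | End of initial trial, after the site's last subject | No; marked X with a footnote, not as an if-applicable item |
| Section 5.4.4, list for continuing subjects | After the site's last subject | Yes |
| Section 5.4.4, list for exiting subjects | Not listed | Not applicable |

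Section 5.4.4 is the outlier.

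**2. Share of sites captured if the 5.4.4 lists are followed**

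Inputs: q, the probability that a site's last subject qualifies, assumed to be 41% to 71% (literature rates in Section 2, which adds that they may be higher); e, the share of non-qualifiers who are extended, not given in the documents.

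Captured share = (1 − q) × e.

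- e = 1 (upper limit): 1 − 0.41 = 59%; 1 − 0.71 = 29%.
- e = 0.5 (illustration): 0.59 × 0.5 = 29.5%; 0.29 × 0.5 = 14.5%.

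**3. What that would do to the test**

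Assumptions: 20 physicians, one per site; exact binomial test; one-sided level 0.025 or 0.05. The tail probability is p = Σ C(n,k) 0.6^k 0.4^(n−k), summed from k = r to n. The numbers captured with e = 1 are 20 × 0.59 = 11.8, about 12, and 20 × 0.29 = 5.8, about 6.

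| Answers | Fewest favouring anatomic to reject H0 | p at that count | Power if true P = 90% |
|---|---|---|---|
| 20 | 17 (85%), either level | 0.016 | 0.867 |
| 12 | 11 (92%), either level | 0.0196 | 0.659 |
| 6 | 6 (100%) at 0.05; impossible at 0.025 | 0.6^6 = 0.0467 | 0.531 at 0.05; 0 at 0.025 |

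**4. Effect of who is counted**

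Suppose 17 of 20 physicians with experience of both techniques prefer anatomic placement: p = 0.016. Now add four physicians who used only one technique.

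- One of the four prefers anatomic: 18/24, p = 0.096.
- Three of the four do: 20/24, p = 0.0134.

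The conclusion can turn on a choice of denominator that the visible text does not make.

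**The case against.** **The rest of the protocol is clear.** Table 2 and Sections 4.3.2 and 5.7 carry no restriction, so a site loses its answer only by following one list and ignoring them. This stands to the extent that a reader who infers that the whole protocol limits the item to extended-period subjects goes too far. The conflict remains, because Section 5.4.4 is the visit instruction for this form.

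**The exit list's clinician assessment may cover preference.** Section 5.7 describes both under one title, so the reading is possible. But Table 2 gives them separate rows, with clinician assessment at implant only, and the other 5.4.4 list names preference separately. The entry does not clearly close the gap.

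**The denominator may be defined elsewhere.** The analysis heading for this endpoint and the case report form appendix have no visible text. A reader might infer that the denominator is wrong, or that a site with several implanters cannot give several answers. The documents support neither; the visible text only leaves the point open. No analysis rule, however, can recover forms that were never collected.

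**Asking after the last subject is sensible.** This is correct. It lets the physician judge on all of the site's cases, and the fix keeps it.

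**Captured physicians have just seen a failure, so answers are biased against anatomic placement.** This is tempting but unsupported. The question asks about all the physician's subjects, and the last subject may be in either arm, so the direction of any bias is unknown.

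**Chance of having used only one technique.** A reader might use 2 × 0.5^n: 50%, 25%, 12.5% and 6% for 2 to 5 cases. That ignores the site blocks. At a single-implanter site with an assumed first block of 4, the chance is 2 × (2/4 × 1/3) = 33% at two cases and zero from three. Block sizes and implanters per site are not visible, so no figure can be given. The possibility remains, because allocation is not balanced within physician.

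**Conclusion.** The concern holds in a limited form. Section 5.4.4 contradicts Table 2 and the end-of-study timing in Sections 4.3.2 and 5.7. Taken literally, it makes collection of the only tested secondary endpoint depend on the last subject's outcome and a discretionary extension. Capture would be at most 59% to 29% of sites. That range assumes that the literature rates in Section 2 apply to this composite, although Section 2 reports no trial-period data for this stimulation mode. Sites that follow Table 2 lose nothing.

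Separately, the visible text does not say which physicians make up P. It is an open question pending the analysis text, not a demonstrated error in the denominator.

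The consequence is confined to the secondary claim. Under Section 6.7, study success rests on the primary endpoint alone. The correction is worth making, since this is the only other hypothesis tested.

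**What to change.** 1. Correct both lists in Section 5.4.4 to match Table 2, and align the wording with the end-of-study timing in Sections 4.3.2 and 5.7.
2. Move the item off the subject visit. Collect one preference form from each implanting physician after the site's last end-of-initial-trial visit, whatever that subject's outcome.
3. Unless the analysis text that is not visible already does so, define P over physicians with at least one study implant in each arm, and report all respondents as a sensitivity analysis.

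The cost is a wording change and one short form per physician. A few low-volume physicians would leave the tested denominator; their answers would still appear in the sensitivity analysis.

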#### **5.4.5 End of Extended Trial Evaluation Period (if applicable)**

Subjects will return to the clinic at the end of the extended trial evaluation period, at which time the subject's participation in the clinical investigation is completed regardless of qualification for permanent implant. Once the subject exits the study, the subject will continue their treatment per the physician's standard of care.

Record the required information on the applicable CRF:

- NRS
- Patient satisfaction and PRP
- Stimulation assessment
- Lead Location
- Adverse events (if applicable)
- Deviations (if applicable)
- Withdrawal (if applicable)
- Death (if applicable)
- Qualify for permanent implant

Upload and attach the following documentation to the applicable CRF:

- Images

During the extended trial evaluation period, the stimulation parameters may be optimized. If this is needed, the subject would return to the clinic for adjustments to the programming parameters.

### **5.5 Unscheduled Visits**

An unscheduled visit is defined as any visit where the subject returns to the participating study site for medical care outside of a specified study visit. Reasons for unscheduled visits may include an adverse event, wound check, or programming change (not protocol specific).

During the trial evaluation period(s), the stimulation parameters may be optimized. If this is needed, the subject would return to the clinic for adjustments to the programming parameters.

Record the required information on the applicable CRF:

- Reason for visit
- Programming time (if applicable)
- Lead Location (if applicable)
- Adverse events (if applicable)
- Deviations (if applicable)
- Withdrawal (if applicable)
- Death (if applicable)

### **5.6 Patient Reported Outcome (PRO) measures**

The Study Coordinator or designee will give the subject questionnaire to complete on his or her own or apply an interview technique. It is important the subject understands the meaning of all words and instructions in the questionnaires. The subject should be instructed to ask any questions about the questionnaires if further explanation is needed. Once the questionnaires are completed, the Study Coordinator or designee will review for completeness to verify that all questions have been answered and only one response is chosen for each question unless otherwise noted.

The following PRO measures will be collected according to the study requirements:

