### 4.3.1 Primary Endpoint

The primary endpoint is the qualification rate for permanent system implant at the end of the initial trial evaluation period.

Qualification for permanent system implant is defined by a composite in which a subject meets all of the following conditions:

- >50% patient reported pain relief (PRP) at the end of the trial evaluation
- Trial evaluation period lasted for a minimum of 3 days
- Physician recommends subject for permanent system implant
- Subject reports a willingness to pursue a permanent system implant

Subjects are not qualified for permanent system implant if they meet **both** of the following:

- ≤50% PRP (patient reported pain relief) at the end of the trial evaluation
- Trial evaluation period lasted for a minimum of 5 days

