##### **4.4.2 Exclusion Criteria**

Patients are not eligible for clinical investigation participation if they meet any of the following exclusion criteria:

1. Patient currently has a spinal cord stimulation system implanted.
2. Patient has previously failed a spinal cord stimulation therapy (either trial system evaluation or permanent system implant).
3. Patient has a primary diagnosis of Peripheral Vascular Disease (PVD), Angina Pectoris, or Chronic Migraine.
4. Patient is scheduled to undergo an on-the-table trial evaluation (aka all-in-one procedure)
5. Patient is scheduled to be implanted with (a) surgical paddle trial lead(s).

6. Patient is currently participating in another clinical investigation with an active treatment arm.
7. Patient is unable to read and/or write.

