#### **5.4.3 Trial System Implant (Initial Trial Evaluation Period Start)**

Record the required information on the applicable CRF:

- Implant procedure and system data
- Stimulation assessment
- Clinician assessment
- Procedure time
- Programming time
- Adverse events (if applicable)
- Deviations (if applicable)
- Withdrawal (if applicable)
- Death (if applicable)

Upload and attach the following documentation to the applicable CRF:

- Images

The subject will complete a Patient Trial Diary once a day utilizing an application located on the Patient Controller during the trial evaluation period. The subject will record areas of pain, stimulation therapy goals and percentage of pain relief in the diary. At the end of the trial evaluation period, the End of Trial Summary report will be submitted to the sponsor.

The following section of the protocol provides a guideline for surgical implantation and programming of the trial evaluation system.

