### **5.6.1 Numerical Rating Scale (NRS)**

The pain NRS consists of 1 question that will be asked by interviewing the subjects. The subjects will be asked to rate their average pain specific to the area(s) of chronic pain being treated over the past 24 hours on a 0 (no pain) to 10 (worst imaginable pain) scale. A higher score indicates a higher pain level. The NRS is implemented in the Baseline CRF, the End of Initial Trial Evaluation Period CRF or the End of Extended Trial Evaluation Period CRF.

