### **5.6.2 Patient Reported Pain relief (PRP)**

Subjects are asked to directly estimate the percentage of pain relief experienced during the trial period from 0% (no pain relief) to 100% (total pain relief). (e.g. "I have 60% pain relief").

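### Patient-reported pain relief, a required part of the primary composite, may be collected by interview, and the protocol does not require the collector to be unaware of allocation

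*Combined protocol and SAP*

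**What the plan says.** Section 4.3.1 makes qualification a composite of four conditions. One is ">50% patient reported pain relief (PRP) at the end of the trial evaluation". The others are a trial of at least 3 days, the physician's recommendation, and the subject's stated willingness. Non-qualification is PRP of 50% or less together with at least 5 days of trial. Section 6.1.1.3 limits the analysis population to subjects who fall in one of these two classes.

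On collection, section 5.6 says staff will "give the subject questionnaire to complete on his or her own or apply an interview technique". It gives no rule for choosing between the two and does not ask for the mode to be recorded. Section 5.6.2 adds only that "Subjects are asked to directly estimate the percentage of pain relief experienced during the trial period", with a 60% answer as its example. By contrast, section 5.6.1 fixes the mode for the NRS: "The pain NRS consists of 1 question that will be asked by interviewing the subjects".

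On blinding, section 5.4.2 blinds the subjects and sends each assignment to the site through the EDC portal. It also states: "Implanting physicians and surgical support staff must follow the specific guidelines for the lead placement techniques and therefore cannot be blinded". A Blinding Plan listing the parties involved is kept as a separate document.

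Two further facts bear on feasibility. Section 4.4.2 excludes anyone meeting the criterion "Patient is unable to read and/or write". Section 5.4.3 describes a daily application on the Patient Controller: "The subject will record areas of pain, stimulation therapy goals and percentage of pain relief in the diary".

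**The concern.** PRP is a single self-rating cut at 50%. A subject hovering near that value can be moved to the other side by tone, prompting or a request to reconsider, with no intent to mislead. If the person asking knows which technique was used, such movement can differ between arms even though the subject remains blinded.

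In a non-inferiority comparison, a push that favours the anatomic arm makes a truly worse technique look acceptable. A push against it costs power. Section 6.2 itself says the primary endpoint depends on the arms being treated alike in everything except the procedure, and an uncontrolled collection mode sits badly with that.

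**Working it through.** **Step 1: what PRP does in the endpoint.** Above 50% is necessary to qualify. At or below 50%, with at least 5 days of trial, defines non-qualification. Read literally with section 6.1.1.3, the 50% cut separates the two analysed classes. It does not settle qualification alone, because the other three conditions must also hold.

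**Step 2: who may collect it, and how.** Section 5.6 permits interview. Section 5.6.2 neither narrows that nor fixes the wording. The collector is the coordinator or a designee, whose blinding status is not stated. The site receives the allocation. The standardized script in sections 5.4.2 and 6.2 is meant to avoid revealing the assignment to the subject; nothing says it governs how PRP is asked.

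**Step 3: whether interview is needed.** The literacy exclusion and the self-entered daily diary suggest that most subjects could complete one percentage item unaided. Table 2 lists PRP and the diary separately, and no section makes the diary value the endpoint.

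**Step 4: hypothetical scale.** The plan has no figure to reproduce: the headings for analysis method and sample size (6.1.1.1, 6.1.1.2, 6.4) have no text beneath them in the public document.

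- From the documents: margin 15 points (6.1.1), 1:1 allocation (5.4.2), and 71% as one end of the literature range (section 2).
- Assumed: one-sided 2.5%, a targeted rate of 65% as a second value, 113 or 174 per arm, a true difference of -15 points, and the sizes of shift.

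Let T be the targeted rate, A = T - 0.15 + s the anatomic rate after a net shift s in that arm only, and n the number per arm. Every moved subject is taken to meet the other conditions.

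SE = √{[T(1 - T) + A(1 - A)]/n}; probability of concluding non-inferiority = Φ[(A - T + 0.15)/SE - 1.960].

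With s = 0 this returns 2.5%. The ends of the range are:

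| s | T | n | A | SE | (A - T + 0.15)/SE | Probability |
|---|---|---|---|---|---|---|
| 0.03 | 0.65 | 113 | 0.53 | 0.0649 | 0.462 | Φ(-1.498) = 6.7% |
| 0.03 | 0.71 | 174 | 0.59 | 0.0507 | 0.591 | Φ(-1.369) = 8.6% |
| 0.05 | 0.65 | 113 | 0.55 | 0.0648 | 0.771 | Φ(-1.189) = 11.7% |
| 0.05 | 0.71 | 174 | 0.61 | 0.0505 | 0.990 | Φ(-0.970) = 16.6% |

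**Step 5: the same nudge in both arms.** Move 5% of non-qualifiers in each arm.

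- T = 0.65, n = 113: T becomes 0.65 + 0.05 × 0.35 = 0.6675 and A becomes 0.50 + 0.05 × 0.50 = 0.525. The difference is -0.1425, SE 0.0646, Φ(0.116 - 1.960) = 3.3%.
- T = 0.71, n = 174: the rates become 0.7245 and 0.582. The difference is again -0.1425, SE 0.0504, Φ(0.149 - 1.960) = 3.5%.

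**Step 6: the opposite direction.** Suppose the arms are truly equal at 41%, 56% or 71%, with 169, 172 or 144 per arm (80% power at one-sided 2.5%, also assumed). A 5-point shift against the anatomic arm lowers power to 45-47%.

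**The case against.** Five points can fairly be made for the plan.

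- **Collector and mode.** A reader might infer that unblinded staff will interview subjects for PRP. The documents do not say that. Where interview is intended, the plan says so (NRS, Stimulation Assessment). The coordinator is not among those named as impossible to blind, and the Blinding Plan and CRFs, which could settle the matter, are not in the public text. This stands: the defect is that interview is permitted and the collector's status is left unstated.
- **PRP as the deciding or only subject-blinded component.** This too might be inferred, and it is wrong. The blinded subject also reports willingness, and the physician's recommendation is required. Implanting physicians cannot be blinded, so that route stays open whatever is done about PRP.
- **Existing safeguard.** The diary gives the sponsor a self-entered record of percentage relief. It could serve as a cross-check, although the plan does not name it as one.
- **Magnitude.** A reader might take 6.7-16.6% as the trial's actual error rate. It is not. It needs steering in one arm only, upward, with a true deficit at the margin. Equal nudging barely moves the error rate.
- **NRS.** Since the NRS is fixed as interview, one might want it changed as well. It is not in the primary composite. It is a descriptive change from baseline, and altering only the end-of-trial mode would build a mode change into that score.

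None of these removes the open route for PRP. Literacy does not prove that every subject can self-complete, so an exception must remain available.

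**Conclusion.** The point holds in limited form. PRP above 50% is a required component of the primary composite, and PRP of 50% or less with the 5-day rule defines non-qualification. Yet the protocol permits interview, fixes no mode for PRP, and does not require a collector who is unaware of allocation. The Blinding Plan may deal with this, but the protocol text does not say so.

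The documents give no estimate of how large any steering would be or which way it would run. The calculated figures show only how sensitive the conclusion is to differential movement at the cut, under an assumed alpha, sample size, targeted rate and true deficit. They are not a forecast, and they are not the gain to be expected from the fix, because the physician's recommendation is untouched. The change is worth making because it closes one avoidable route at very little cost.

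**What to change.** In sections 5.6 and 5.6.2:

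- Require PRP at the end of the initial trial evaluation, and of the extended one where it applies, to be completed by the subject on paper or on the Patient Controller before any discussion of results with the physician or programming staff.
- Put the subject's willingness item on the same self-completed form.
- Allow interview only as an exception, recorded on the CRF, and report the number of exceptions by arm.
- Leave the NRS as an interview item at every time point so that baseline and follow-up match.

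The cost is a CRF instruction and site training, plus slightly more checking for unanswered items. No additional visit, assessor or sample size is needed.
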